11.6. Data Monitoring Committee

An independent DMC consisting of one Biostatistician and two clinicians that includes at least one Oncologist with expertise in head and neck cancer will be formed to monitor the safety and conduct of the study on an ongoing basis. Parameters to be evaluated will include AEs (clinical and laboratory), number of dropouts overall, those withdrawals specifically due to worsening of disease, and those withdrawals due to failure to improve in a timely fashion. Data will be presented as to the DMC as treatment groups A and B to maintain the study blind. However, the DMC, as part of its charter to evaluate and ensure the safety of subjects participating in the trial, has the authority to unblind the data as appropriate.

Original: 11 January 2017 Confidential Page 55 of 67

The DMC may request any safety data including, but not limited to, SAEs, AEs, and laboratory values. The DMC may also request any efficacy data including, but not limited to the primary and secondary outcomes to evaluate benefit to risk.

The DMC will review unblinded data at the interim analyses and make recommendations to halt the trial for overwhelming efficacy, or safety concerns, or for futility; continue the trial as written; or resize the trial based on the placebo duration of SOM.

[figure not shown]

12. STATISTICS

12.1. Overview

Complete details of analyses and relative order of importance of each analysis are more fully delineated in the Statistical Analysis Plan.

Given the anticipated non-Gaussian distribution of values for duration of OM, the severity-weighted OM calculations (AUC), and the days to onset of OM, treatment groups will be compared for these variables using a log-rank test of the differences in the duration of SOM between the SGX942 and placebo treated groups. The incidence of OM, percent of RECIST complete responders, and percent of patients with each category of infection will be compared using chi-squared tests. The primary analysis population will be patients who have received enough radiation exposure to put them at significant risk of developing SOM (defined as a cumulative radiation dose of at least 55 Gy).

Original: 11 January 2017 Amendment 1: 29 November 2017

Amendment 2: 22 January 2018 Amendment 3: 17 September 2019

12.3. Final Analysis

Upon completion of enrollment, the study database is to be locked, released, and analyzed in two parts, the first being an analysis of data through the 6-week visit from the last RT for the last patient, and the second final analysis of all data including all long-term visit data. During these two data analyses, all site personnel will remain blinded as to individual patient dose-group assignments.

12.4. Sample Size Calculation

Sample size assessments are based on testing the hypothesis of superiority with a two-sample log rank test using the median duration of SOM, an equal allocation ratio, a 90% power $(1-\beta)$, and an α level of 0.05. In the Phase 2 clinical trial, the median duration of SOM was 30 days in the placebo group and 10 days in the 1.5 mg/kg SGX942 treatment group. Because of the variability of reported results for SOM in patient population, a conservation assumption was made that the median duration of SOM among patients receiving a minimum of 55 Gy of cumulative radiation will be 13 days in the placebo group and 8 days in the SGX942 group. Using this assumption, approximately 95 evaluable patients per arm (190 patients total) will need to complete the trial.

12.5. Selection of Primary Analysis Population

Given that OM does not occur at a significant rate in patients that have not received at least 55 Gy of cumulative radiation, the primary analysis population will be limited to those patients that have received at least 55 Gy of radiation. Only those patients that receive sufficient radiation therapy are at risk of developing the disease (i.e., SOM). Should SGX942 reduce the most severe cases of OM prior to reaching 55 Gy of radiation such that there is a reduced dropout rate from anticancer therapy, the worst cases of OM in the placebo group, but not the SGX942 group, will be eliminated from the analyses. Thus, if bias is introduced, it is likely to lead to a conclusion that SGX942 is less efficacious than it actually is.

The primary efficacy analysis will be based on this mITT population that is defined as all randomized subjects receiving a minimum of 55 Gy of cumulative radiation analyzed per treatment groups defined by their randomization treatment assignment.

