### 2.2.2 Other Secondary Endpoints

- Comparison of the cumulative number of days of RT breaks (mITT population)
- Comparison of the duration of SOM; in all randomized patients receiving fractionated RT and concomitant cisplatin chemotherapy, given as 80-100 mg/m² (ITT population)
- Comparison of the duration of UOM (mITT population)
- Comparison of the cumulative amount of pain reported by patients (mITT population)

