## 3.3 METHODOLOGY AND CONVENTIONS

Safety and efficacy data will be summarized and presented by treatment group (SGX942 and placebo) in summary tables. Continuous variables will be presented by descriptive statistics including n, mean, standard deviation, median, minimum, and maximum. Categorical variables will be tabulated by frequency count and percentage.

Unless otherwise stated, all statistical tests will be two-sided hypothesis tests performed at the 5% level of significance for main effects, and all confidence intervals will be two-sided 95% confidence intervals. All analyses will be performed using SAS® Version 9.3 or higher.

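### The primary population is selected by reaching 55 Gy after randomisation; Protocol 12.5's argument on the direction of bias covers one scenario only, and the ITT analysis that could check it is ungated and has no rule for disagreement.

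*Protocol*

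**What the plan says.** Protocol 12.5 restricts the primary analysis to randomised patients who received at least 55 Gy. SAP 3.2.3 adds at least one dose of study drug. Two statements in 12.5 support the choice. The first is that "OM does not occur at a significant rate in patients that have not received at least 55 Gy". The second is a scenario that begins "Should SGX942 reduce the most severe cases of OM prior to reaching 55 Gy of radiation": fewer SGX942 patients then abandon anticancer therapy, the worst placebo cases are lost, and so "if bias is introduced, it is likely to lead to a conclusion that SGX942 is less efficacious than it actually is".

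The ITT comparison is planned. SAP 2.2.2 and 9.3.2 list it among the other secondary endpoints ("Comparison of the duration of SOM; in all randomized patients receiving fractionated RT and concomitant cisplatin chemotherapy"), Protocol 10.2.2.2 does the same, and SAP section 9 repeats the efficacy assessments in ITT and PP as sensitivity analyses. The five gated secondaries in SAP 9.3.1 are all in mITT. Protocol 10.2.2.2 defines ITT as everyone randomised, whereas SAP 3.2.2 requires at least one dose.

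**The concern.** Reaching 55 Gy happens after randomisation, and 12.5 itself allows that SGX942 may change who reaches it. The two arms of the mITT set may therefore not be comparable.

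The defence reasons from a drug that works. Type I error concerns a drug that does not, and the argument is silent there. Its two statements also pull against each other. If little OM occurs below 55 Gy, severe OM can hardly drive patients out before that dose. If severe OM does drive them out, the excluded patients were at risk of the outcome after all.

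What is at stake is the reading of a positive primary result. If early stopping differs by arm among the worst cases, mITT alone cannot separate a drug effect from selection. The analysis that could help has no formal standing when the two disagree.

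**Working it through.** **1. The plan's own figure.** Inputs from Protocol 12.4: "an equal allocation ratio, a 90% power", "an α level of 0.05", and medians that "will be 13 days in the placebo group and 8 days in the SGX942 group". SAP 3.3 gives the sidedness: "all statistical tests will be two-sided hypothesis tests performed at the 5% level of significance".

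- Ratio r = 8/13 = 0.615.
- Freedman events = (1.960 + 1.282)² × ((1 + r)/(1 − r))² = 10.51 × (21/5)² = 10.51 × 17.64 = 185.4, so 186.
- With exponential durations and an assumed 63 days of observation, 98.05% of episodes resolve: 186/0.9805 = 189.7. The plan states 190, so the figure is reproduced.
- Enrolment is 260, so (260 − 190)/260 = 26.9% could be non-evaluable with 190 still left. No loss rate before 55 Gy is stated, overall or by arm. SAP section 2 says only that such dropouts may increase during the pandemic.

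**2. Bias when the drug does nothing.** Assumptions: 130 per arm, 85% SOM incidence, overall median 13 days in both arms, non-cases at 0.01 days, censoring at 63 days, 4,000 simulated trials, log-rank test. A two-sided 5% test should favour SGX942 in 2.5% of trials. Assumed loss before 55 Gy is 6% outside the worst third (by SOM duration). Within the worst third it is 15% on placebo and 30% on SGX942.

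- Placebo excluded: 0.15/3 + 0.06 × 2/3 = 9%.
- SGX942 excluded: 0.30/3 + 0.06 × 2/3 = 14%.

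| Loss pattern, no drug effect | mITT favours SGX942 |
|---|---|
| 9% placebo v 14% SGX942 | about 7% to 8.3% over repeated runs |
| Same rates, arms reversed | 0.6% to 0.8% |
| 7% v 14% | 11% to 12% |
| All randomised kept and fully observed | 2.2% to 2.7% |

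(With 6% elsewhere, 7% overall on placebo means (0.07 − 0.04) × 3 = 9% of its worst third.)

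**3. Other patterns.** A second set-up has exponential durations, SOM in every patient, and 10% loss except where stated.

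- Protocol's scenario (true medians 13 v 8; 20% to 60% of the longest-SOM placebo third lost): mITT power falls from 90.6% to 25.4%, against about 97% in all randomised. Bias is against SGX942.
- No effect, 20% to 60% of the longest-SOM SGX942 third lost: 5.4% to 55.1% favour SGX942.
- No effect, 20% to 40% of the shorter-SOM two thirds of placebo lost: 5.1% to 18.8%.
- No effect, equal severity-related loss (10% and 60% in both arms): 2.6%, no inflation.
- No effect, loss unequal but unrelated to severity (15% v 35%): 2.7%, no inflation.

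**4. Does ITT guard against this as written?** Protocol 7.3 ends OM scoring at withdrawal and censors the patient. Protocol 10.1 and SAP 9.1 give anyone without SOM a duration of 0.01 days, the best possible outcome. On its face this covers a patient who left before SOM could appear. In the 9% v 14% case, if all early stoppers leave mid-episode, ITT favours SGX942 in 2.3% of null trials. If half leave before SOM, the figure is about 6% to 7%, and about 9% in the 7% v 14% case.

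**5. Cost of a gate.** At the design effect, mITT succeeds in 86% of simulated trials, and mITT and ITT both succeed in 84%.

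**The case against.** The strongest reply is that 12.5 is being held to more than it says. A reader might infer that it claims bias can only hurt SGX942. The text says likely, and it is conditional on the drug reducing severe OM. Within that scenario the argument is right, as step 3 shows. It is incomplete rather than false. Nor is the paragraph strictly self-contradictory: a low rate of OM below 55 Gy does not exclude some severe early cases. It is a tension that leaves the scenario poorly supported.

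A reader might also infer that ITT has no place in the plan. It is both a prespecified other secondary endpoint and a sensitivity analysis. The gap is narrower: no position in the gated sequence, no rule for discordance, and two definitions.

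The inflation depends on assumed losses. A doubling in the worst third (15% v 30%) with no effect on SOM is a strong assumption behind modest-looking totals, and the documents offer no mechanism for it. SAP section 4 already reports population counts and discontinuation reasons.

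All of this stands and limits the claim. It does not make the direction of bias predictable, and it gives no rule for a positive mITT result that ITT fails to support.

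**Conclusion.** The concern holds in limited form. The primary set is selected after randomisation, and the reassurance in 12.5 covers one pattern of loss. Under another pattern the bias favours SGX942: about 7% to 8% against 2.5% with assumed exclusions of 9% v 14%. That size rests on assumed loss rates, 85% incidence and exponential durations. The firm finding is that either direction is possible. Bias needs loss that is related to SOM severity and differs by arm. Without both, there is no inflation.

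A reader might infer that gating ITT would restore the primary test's error rate. It would not, because mITT remains primary and its own error is unchanged. The gate limits the secondary claims, and the reading rule limits what a positive mITT result is taken to show. ITT serves as that check only if patients who leave before SOM are not scored as best outcomes. This is a cheap improvement that should be made. It does not show that the trial is biased.

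**What to change.** - Keep mITT as primary.
- In Protocol 12.5, replace the direction-of-bias sentence with a statement that selection on reaching 55 Gy could bias the result either way.
- Put ITT duration of SOM first in the gated sequence of SAP 2.2.1 and 9.3.1. State that a positive mITT result not supported by ITT will not be read as robust evidence of efficacy.
- Align SAP 3.2.2 with Protocol 10.2.2.2, so that ITT means all randomised patients.
- In the ITT analysis, do not count patients who leave before any SOM as 0.01-day events, or add a sensitivity analysis without that rule.
- Tabulate patients below 55 Gy by arm, reason and last WHO grade, extending the disposition tables in SAP section 4.

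The cost is Protocol and SAP wording, one table, and one extra gate before the AUC comparison. The added power loss for the secondary claims is small: in the design-effect run, the chance of reaching AUC testing falls from 86% to 84%.

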12.6. Direct Access to Source Data/Documents

It is the responsibility of the Principal Investigator (PI) and the participating institution to assure that appropriate trial-related monitoring, audits, IRB/EC review, and regulatory inspection(s) can be carried out by assuring direct access to source data/documents.

12.6.1 Study Monitoring

It is the responsibility of the PI and site personnel to assure that the data recorded in the CRFs are accurate, complete, and can be verified from the medical records.

Original: 11 January 2017 Confidential Page 58 of 67

In accordance with the Guidelines for the Monitoring of Clinical Investigations presented in the International Conference on Harmonisation (ICH) Guidance on GCPs (E6), Soligenix will select, either directly or through subcontract, qualified individuals to monitor the progress of the study and adherence to protocol by the individual clinical sites.

12.6.2 **Pre-study Evaluation**

This initial encounter with the site will establish that the site has all of the necessary elements to successfully participate in the proposed protocol including adequate trained staff, adequate free time of the staff, adequate facilities for safe and proper trial conduct, evidence for potential enrollment of suitable patients, adequate research pharmacy support, the presence of an IRB/EC meeting the local and FDA requirements, and a commitment for training of all involved staff on the protocol.

12.6.3 **Site Initiation Visit**

The Medical Monitor (or trained designee) will initiate the study after on-site training of the participating staff at the institution. Topics covered will include training on:

- The investigational status of the study drug and the requirements for its accountability
- Background on the study drug
- Details of the protocol including patient selection, study drug administration, procedures to be performed, and visit schedules
- Critical nature of obtaining informed consent in accordance with the Declaration of Helsinki and ICH Guidance on GCPs (E6) before enrolling each subject in the study
- The obligation to ensure IRB review and approval for the study, including the protocol, amendments, ICF and any advertisements, is obtained prior to its initiation at his/her clinical site, to ensure continuing review of the study by the IRB, and to keep Soligenix informed of such approval and subsequent actions concerning the study

12.6.4 **Monitoring Visits**

Soligenix or their trained designee will perform on-site monitoring visits as frequently as it deems necessary. At these visits, the site monitor will compare the data entered into the eCRF with the source documents and check for protocol compliance including a record of informed consent, enrollment criteria, all subject assessments, all adverse experiences, and all concomitant medications. In addition, study drug and supporting records will be reviewed. Additionally, they assure that all serious, life-threatening or fatal adverse experiences are being reported immediately [and in no case later than twenty-four (24) hours after the event] to the Medical Monitor or designee at Soligenix.

Findings from these reviews will be discussed with the investigator and staff. Completed pages of the eCRF will be evaluated at each visit. The dates of the monitoring visits will be recorded in a sign-in log that will be kept at the site. The study coordinator and investigator are expected to be available for questions, the source documentation readily available, and a suitable environment provided for review of study-related documents.

Original: 11 January 2017

12.6.5 Close-out Visit

The clinical research monitor(s) will perform an end of trial visit to ensure that:

- All drug reconciliation forms are accurate and complete.
- All unused study drug is returned to the appropriate location.
- All data issues are resolved and eCRF are completed and verified.
- The IRB has been notified that the study has been completed.
- The investigator at each site is aware that the study has been completed and no further subjects are enrolled.

12.7. Audits and Inspections

Health Authorities (e.g., FDA, the EMA, or country Health Authorities), in the person of a trained and properly authorized employee, may request access to all study records, including source documents, for inspection and copying. The investigator will immediately notify Soligenix of any upcoming inspections.

Periodic auditing inspections may also be conducted by a representative of the Quality Assurance Department of Soligenix or its trained designee(s).

13. INSTITUTIONAL REVIEW BOARD (IRB)/ETHICAL COMMITTEE (EC)

All participating centers must have in place either an IRB or the EC that meets all of the criteria outlined in Section 3 of the ICH "Guidance for Industry; E6 Good Clinical Practice: Consolidated Guidance". Copies of the IRB/EC membership list and procedures should be provided to the Soligenix.

It is the responsibility of the site's Principal Investigator (PI) to obtain IRB/EC written approval of the protocol, the Informed Consent Form, patient compensations details, and any advertisements to be used in conduct of the trial. No patient can be enrolled into the trial prior to obtaining these documents. It is also the site's PI responsibility to:

Assure that no deviations from, or changes of, the protocol should be initiated without prior written IRB/EC approval/favorable opinion of an appropriate amendment, except when necessary to eliminate immediate hazards to the subjects or when the change(s) involves only logistical or administrative aspects of the trial (e.g., change of monitor(s), telephone number(s))

Promptly report to the IRB/EC:

- All deviations from, or changes to, the protocol to eliminate immediate hazards to the trial subjects
- Any changes increasing the risk to subjects and/or affecting significantly the conduct of the trial
- All AEs that are both serious and unexpected whether seen at that institution or reported from Soligenix
- Any new information that may affect adversely the safety of the subjects or the conduct of the trial.

14. QUALITY CONTROL AND QUALITY ASSURANCE

It is the responsibility of the PI or his/her designee to assure that all information in the eCRF is accurate and complete. The eCRF will perform immediate internal consistency checks to minimize potential for erroneous data (e.g., date of birth after date of randomization). Soligenix will use monitors to review entered data in the eCRF and make periodic site visits to compare eCRF data with source documents. Periodic interim audits from Soligenix's Quality Department or their designee will be conducted to assure that all ICH guidelines are being followed and identify any systemic problems with the data or procedures. Final audits will be conducted at representative sites.

Confidential

Amendment 2: 22 January 2018 Amendment 3: 17 September 2019

15. ETHICS

15.1. Ethical Review of Trial

The final study protocol, including the final version of the Subject Information and Consent Forms, must be approved in writing by IRB/EC before enrollment of any subject into the study. The PI or their designee is responsible for informing the IRB/EC of any SAEs and amendment(s) to the protocol as per regulatory requirements.

15.2. Ethical Conduct of the Study

The study will be performed in accordance with the ethical principles in the Declaration of Helsinki, GCPs and applicable regulatory requirements.

15.3. Written Informed Consent

The Investigator will ensure that the subject or a legally authorized representative of the subject are given full and adequate oral and written information about the nature, purpose, possible risks and benefits of the study. Subjects must also be notified that they are free to discontinue from the study at any time. The subject should be given the opportunity to ask questions and allowed time to consider the information provided. *The subject's signed and dated informed consent must be obtained before conducting any study specific procedure*. The consent form that is used must meet the requirements as outlined in the ICH Guidance on GCPs (E6) and must be approved by both the reviewing IRB/EC and by Soligenix.

15.4. Subject Data Protection

The Subject Information and Consent Form will explain that study data will be stored in a computer database, maintaining confidentiality. Subjects in this database will be identified by initials or enrollment code/subject number only. An authorized representative of a regulatory authority may require direct access to parts of the trial site records relevant to the study, including subjects' medical history for data verification purposes.

15.5. Financial Disclosure

The FDA has issued regulations (21 CFR Part 54) that require Sponsors (in this case Soligenix) to submit complete and accurate certification or disclosure statements to certify the absence of certain financial interests of clinical investigators and/or disclose those financial interests, as required, when clinical studies are submitted to the FDA in support of marketing approval of a new drug application (NDA). These regulations are intended to ensure that financial interests and arrangements of clinical investigators, that could affect reliability of data submitted to the FDA in support of marketing approval, are identified and disclosed by the Sponsor.

Regardless of the location of the clinical site, all clinical investigators participating in this clinical trial shall be asked to disclose proprietary (e.g., patent, licensing agreement) and financial (e.g., stock options, royalty) interests as they pertain to Soligenix, prior to participating in the study. In addition, clinical investigators will be required to consult with Soligenix before acquiring any financial interest in the company and must disclose any change in their proprietary

Original: 11 January 2017 Confidential Page 63 of 67

or financial interests if it occurs during the course of the study and for one year following study completion. Clinical investigator is defined under Title 21 CFR Part 54 as an investigator or sub-investigator listed on the FDA Form 1572 that is directly involved in the treatment or evaluation of research subjects. The requirement for proprietary and financial disclosure also includes any ownership by the spouse or any dependent child of the investigator.

If the FDA determines that the financial interests of any clinical investigator raise serious questions about the integrity of the data, the FDA will take any action it deems necessary to ensure the reliability of the data, including:

Initiating agency audits of the data derived from the clinical investigator in question;

Requesting that the Sponsor submit further analyses of data, e.g., to evaluate the effect of the clinical investigator's data on overall study outcome;

Requesting that the applicant conduct additional independent studies to confirm the results of the questioned study; and/or

Refusing to treat the covered clinical study as providing data that can be the basis for an agency action.

If the Sponsor does not include certification or disclosure, or both, if required, or does not certify that it was not possible to obtain the information, the FDA may refuse to file the NDA.

